### **On-treatment assessment/event and observation periods**

For safety summaries, the overall observation periods will be divided into three mutually exclusive segments:

1. **Pre-treatment period:** from day of patient’s informed consent to the day before first administration of study treatment.

2. **On-treatment period:** from date of first administration of study treatment to 30 days after date of last actual administration of any study treatment (including start and stop date)
3. **Post-treatment period:** starting at day 31 after last administration of study treatment.

Safety summaries (tables, figures) include only data from the on-treatment period with the exception of baseline data which will also be summarized where appropriate (e.g. change from baseline summaries). In addition, a separate summary for death including on treatment and post treatment deaths will be provided. In particular, summary tables for adverse events (AEs) will summarize only on-treatment events, with a start date during the on-treatment period (*treatment-emergent* AEs).

However, all safety data (including those from the post-treatment period) will be listed and those collected during the pre-treatment and post-treatment period will be flagged.

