### **Concomitant medications**

Concomitant therapy is defined as all interventions (therapeutic treatments and procedures) other than the study treatment administered to a patient coinciding with the study treatment period. Concomitant therapy include medications (other than study drugs) starting on or after the start date of study treatment or medications starting prior to the start date of study treatment and continuing after the start date of study treatment.

Concomitant medications will be coded using the World Health Organization (WHO) Drug Reference Listing (DRL) dictionary that employs the WHO Anatomical Therapeutic Chemical (ATC) classification system and summarized by lowest ATC class and preferred term using frequency counts and percentages. Surgical and medical procedures will be coded using MedDRA and summarized by SOC and preferred term, Outputs will be summarized, and listed by dose for Part A, Part B, Part C, Part D, and by disease cohorts. The summary of concomitant medications will show the number and percentage of patients taking concomitant medications by Ingredient. Multi-ingredient products will be summarized by their separate ingredients rather than as a combination of ingredients. These summaries will include:

1. Medications starting on or after the start of study treatment but no later than 30 days after start of last dose of study treatment and

2. Medications starting prior to start of study treatment and continuing after the start of study treatment.

In the summary of concomitant medications, each patient is counted once within each unique ingredient. For example, if a patient takes Amoxicillin on two separate occasions, the patient is counted only once under the ingredient “Amoxicillin”. All concomitant therapies will be listed by dose level for Part A and Part C and by disease cohort for Part B and Part D. Any concomitant therapies starting and ending prior to the start of study treatment or starting more than 30 days after the last date of study treatment will be flagged in the listing. The safety population will be used for all concomitant medication tables and listings.

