**5.1.2 AE, ConMeds and safety assessment date imputation**

**Table 5-1 Imputation of start dates (AE, CM) and assessments (LB, EG, VS)**

Missing Element	Rule
day, month, and year	
 
No imputation will be done for completely missing dates
 

day, month	
 
If available year = year of study treatment start date then                             
 
If stop date contains a full date and stop date is earlier than study treatment start date then set start date = 01JanYYYY
 
Else set start date = study treatment start date.
 
 
 
If available year > year of study treatment start date then 01JanYYYY
 
If available year < year of study treatment start date then 01JulYYYY
 

day	
 
If available month and year = month and year of study treatment start date then                             
 
If stop date contains a full date and stop date is earlier than study treatment start date then set start date= 01MONYYYY.
 
Else set start date = study treatment start date.
 
 
 
If available month and year > month and year of study treatment start date then 01MONYYYY
 
If available month and year < month year of study treatment start date then 15MONYYYY
 

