**Table 5-2 Imputation of end dates (AE, CM)**

Missing Element	Rule (* = last treatment date plus 30 days ( not death date, cut-off date, withdrawal of consent date))
day, month, and year	
 
Completely missing end dates (incl. ongoing events) will be imputed by the end date of the on-treatment period*
 

Missing Element	Rule (* = last treatment date plus 30 days ( not death date, cut-off date, withdrawal of consent date))
day, month	

• If partial end date contains year only, set end date = earliest of 31DecYYYY or end date of the on-treatment period *

day	

• If partial end date contains month and year, set end date = earliest of last day of the month or end date of the on-treatment period*

Any AEs and ConMeds with partial/missing dates will be displayed as such in the data listings.

Any AEs and ConMeds which are continuing as per data cut-off will be shown as 'ongoing' rather than the end date provided.

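### Table 5-1 ignores a month-year stop date, so a record with a year-only start that is known to have ended before the first dose is given the treatment start date

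*SAP*

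**What the plan says.** SAP Section 5.1.2 imputes partial dates of adverse events (AEs) and concomitant medications.

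- **Table 5-1, day and month of the start missing, year equal to the year of treatment start.** The stop date is consulted under one condition: "If stop date contains a full date and stop date is earlier than study treatment start date then set start date = 01JanYYYY". Otherwise: "Else set start date = study treatment start date".
- **Table 5-1, only the day missing.** The same full-date test appears, but under this condition: "If available month and year = month and year of study treatment start date then".
- **Table 5-2, stop date with month and year.** "If partial end date contains month and year, set end date = earliest of last day of the month or end date of the on-treatment period".
- **Section 2.1.1, observation periods.** The on-treatment period runs "from date of first administration of study treatment to 30 days after date of last actual administration of any study treatment". AE tables "will summarize only on-treatment events, with a start date during the on-treatment period", with no condition on the end date.
- **Section 2.4.2, concomitant medications.** The first of two inclusion criteria is "Medications starting on or after the start of study treatment but no later than 30 days after start of last dose of study treatment". The second covers medications begun before treatment and continued into it. Therapies that both began and ended before treatment are only flagged in the listing.

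Section 5.1 allows imputed dates to be used for slotting data into study periods.

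**The concern.** Defaulting an uncertain start to the treatment start date is a normal conservative choice when the timing is unknown. Here it is known. The SAP itself accepts that a stop date before treatment should override the default, but it recognises that evidence only in a full date. A stop of 20MAR2016 is handled correctly. A stop of MAR2016, which proves the same thing when treatment starts in June, is not.

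The two tables then give the record a start after its end. Because both counting rules in Sections 2.1.1 and 2.4.2 look at the start date, nothing downstream removes it. A past medication would appear as on-treatment use in the concomitant medication table. It could also enter the table of prohibited medications, which Section 2.4.2 selects by programming. Section 5.1.1 does compare an imputed dose end date with treatment start, but no such check is stated for AE or medication dates.

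**Working it through.** The SAP states no figure to reproduce. The check applies Tables 5-1 and 5-2 literally to worked dates. The dates are illustrative assumptions: treatment start 15JUN2016, last dose 15JUN2017, record start known only as 2016.

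| Recorded stop | Table 5-1 start | Table 5-2 end | Slotted as |
|---|---|---|---|
| 20MAR2016 (full) | 01JAN2016 | 20MAR2016 (as recorded) | pre-treatment, correct |
| FEB2016 | 15JUN2016 | 29FEB2016 | on-treatment, end before start |
| MAR2016 | 15JUN2016 | 31MAR2016 | on-treatment, end before start |
| 2016 (year only) | 15JUN2016 | 31DEC2016 | on-treatment, end not known to be before treatment |
| missing or ongoing | 15JUN2016 | 15JUL2017 (last dose + 30 days) | on-treatment, end not known to be before treatment |

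**Size of the inversion.** From 29FEB to 15JUN is 31 (March) + 30 (April) + 31 (May) + 15 = 107 days. From 31MAR to 15JUN is 30 + 31 + 15 = 76 days.

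**How regular it is.** With treatment starting 15JUN2016, a month-year stop proves a pre-treatment end when the stop month is January to May. Those months have 31 + 29 + 31 + 30 + 31 = 152 days. The true start/stop pairs with start on or before stop number 152 × 153 / 2 = 11,628.

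- Start recorded as year only: all 11,628 pairs are imputed to 15JUN2016.
- Start recorded with month and year: 0 of 11,628 are.

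**Why other rows are unaffected.**

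- In the day-only row the full-date test applies only when the start month is the treatment-start month. A month-year stop in an earlier month would precede the record's own start, so it cannot occur. Starts in earlier months go to the 15th of that month, which is pre-treatment.
- Starts known only to an earlier year go to 1 July of that year, which is also pre-treatment.
- When treatment starts in January there is no earlier month in that year, so no case arises.

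**Check of the fix.** If the latest possible date of the stop is tested, start 2016 with stop FEB2016 gives 29FEB2016 < 15JUN2016, so the start becomes 01JAN2016. The record is pre-treatment and consistent with the Table 5-2 end of 29FEB2016.

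**The case against.** The main arguments on the other side, and what stands of each:

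- **Narrow scope.** A reader might infer that any partial stop date showing a pre-treatment end is mishandled. The document does not support that. It takes a year-only start, in the treatment-start year, with a month-year stop in an earlier month. This limit stands in full.
- **AE tables.** A reader might also infer that pre-treatment AEs would noticeably contaminate the safety tables. The pre-treatment period runs only from consent to the day before first dose. An affected AE must fall there, have a known stop month but an unknown start month, and end in a calendar month before that of first dose. This is possible but very rare.
- **Durations.** Section 5.1 says that imputed partial dates are in general not used for study day, duration or elapsed time. Listings show the partial dates as collected. The inversion therefore affects slotting only. This stands.
- **Definition of concomitant therapy.** Section 2.4.2 opens by requiring overlap with the treatment period, which such a record lacks. The operational criterion that follows still admits it on its imputed start date, so the general definition does not cure the problem.
- **Other summaries.** Prior anti-cancer therapy is summarised separately, and medications that may affect PK or efficacy are identified before database lock rather than taken directly from Table 5-1. This reduces the reach of the error.
- **Order of the tables.** If Table 5-2 ran first and its result counted as a full date, the problem would vanish. The SAP states no order, and the condition reads most naturally as referring to the collected date. This is a reason to clarify the text, not to leave it.

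**Conclusion.** The point holds in its narrow form. In one row of Table 5-1, a record that the data show to have ended before the first dose is assigned the treatment start date, and Table 5-2 places its end before that start. The record is then counted as on-treatment.

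The size of the effect on the tables cannot be computed, because the SAP gives no number of such records. Within the affected configuration the rule errs every time, but how common that configuration is remains unknown. In a cohort of 10, the minimum planned for each Part B cohort and for LCH in Part D, one wrongly counted patient moves a row by 1/10 = 10 percentage points. It moves nothing if the patient also took the same ingredient on treatment, since each patient counts once per ingredient.

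The conclusion assumes that the full-date test refers to the collected stop date. This is a minor correction, mainly for concomitant medications. It does not call the efficacy, dose-finding or main safety conclusions into question.

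**What to change.** In the Table 5-1 row for a missing day and month, replace the full-date condition. The start should be set to 1 January of the recorded year whenever the recorded stop date, full or partial, has a latest possible date earlier than the start of study treatment. For a month-year stop, the latest possible date is the last day of that month. The default to treatment start stays for all other records, and the day-only row needs no change.

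A general rule that an imputed start may not exceed the imputed stop should **not** be added. Table 5-2 caps missing and ongoing stops at last dose + 30 days. With last dose 15JUN2017, an AE with start 2018 and no stop date is given start 01JAN2018, correctly post-treatment, and end 15JUL2017. Forcing the start back to 15JUL2017 would make it treatment-emergent. Any consistency check should compare the imputed start only with the recorded stop date, full or partial.

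The cost is one sentence in the SAP and a small programming change.

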**Table 5-2 Imputation of end dates (AE, CM)**

Missing Element	Rule (* = last treatment date plus 30 days ( not death date, cut-off date, withdrawal of consent date))
day, month, and year	
 
Completely missing end dates (incl. ongoing events) will be imputed by the end date of the on-treatment period*
 

Missing Element	Rule (* = last treatment date plus 30 days ( not death date, cut-off date, withdrawal of consent date))
day, month	

• If partial end date contains year only, set end date = earliest of 31DecYYYY or end date of the on-treatment period *

day	

• If partial end date contains month and year, set end date = earliest of last day of the month or end date of the on-treatment period*

Any AEs and ConMeds with partial/missing dates will be displayed as such in the data listings.

Any AEs and ConMeds which are continuing as per data cut-off will be shown as 'ongoing' rather than the end date provided.

### 5.1.3 Other imputations

#### **Incomplete date of initial diagnosis of cancer and date of most recent recurrence**

Missing day is defaulted to the 15th of the month and missing month and day is defaulted to 01-Jan.

#### **Incomplete assessment dates for tumor assessment**

All investigation dates (e.g. MRI scan, CT scan) must be completed with day, month and year. If one or more assessment dates are incomplete but other investigation dates are available, this/these incomplete date(s) are not considered for calculation of the assessment date and assessment date is calculated as the latest of all investigation dates (e.g. MRI scan, CT scan) if the overall response at that assessment is CR/PR/SD/UNK. Otherwise – if overall response is progression – the assessment date is calculated as the earliest date of all investigation dates at that evaluation number. If all measurement dates have no day recorded, the 1st of the month is used. If the month is not completed, for any of the investigations, the respective assessment will be considered to be at the date which is exactly between previous and following assessment. If a previous and following assessment is not available, this assessment will not be used for any calculation.

#### **Applying the cut-off to tumor assessment**

For tumor related assessments, if an evaluation has some assessments done prior to cut-off date and others after the cut-off date, then the evaluation is considered post-cut-off date and will be excluded from analysis.

### 5.1.4 Age calculation in Lab data

Following algorithm will be applied to derive the age at each visit in the Lab dataset and will be used in mapping the Lab normal reference ranges per age.

#### Step 1

For screening visit:

Use the age that the site provided in raw data (Age in Days, Age in Months, Age in Years)

Age in month will be age in days/30.4375.

Age in month will floor to integer, for example, if the calculated age in month is 14.3 then the age will be considered as 14 months and will be used when mapping with local reference ranges.

For other visits:

If Age is provided in Days, Age at each visit calculated as [Date of sample Collection(LBDT) - ICF date + Age in Days]

If Age is provided in Months, Age at each visit is calculated as [Date of sample Collection(LBDT) - ICF date + Age in Months + 15 days]

If Age is provided in Years, , Age at each visit is calculated as [Date of sample Collection(LBDT) - ICF date + Age in Years + 6 months].

If age is missing in demo then age in each visit is calculated as [Date of sample Collection(LBDT) - ICF date.

Age in month will be age in days/30.4375.

## Step 2

If reference ranges are not mapped and still missing from Step 1, apply the following rules. If Age is provided in Days, Age at each visit = [Date of sample Collection(LBDT) - ICF date + Age in Days]

If Age is provided in months, Age is [Date of sample Collection(LBDT) - ICF date + Age in Months - 15 days] <= Age at each visit < [Date of sample Collection(LBDT) - ICF date + Age in Months + 15 days]

If Age is provided in years, Age is [Date of sample Collection(LBDT) - ICF date + Age in Months - 6months] <= Age at each visit < [Date of sample Collection(LBDT) - ICF date + Age in Months + 6months]

For both cases above, when there are more than one age ranges, select the ranges in order of (1) lower range (2) upper range. For example, if the age ranges are 13-60 and 61-119, then choose 13-60.

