#### General analysis conventions

**Pooling of center:** Unless specified otherwise, data from all study centers will be pooled for the analysis. Due to expected small number of patients enrolled at centers, no center effect will be assessed.

**Qualitative data:** (e.g., gender, race, etc.) will be summarized by frequency counts and percentages by study parts and by dose for Part A and Part C dose exploration, by age (<2 years, 2 to <6, 6 to <12, and 12 to 18 years) for Part A age expansion, by disease cohorts for Part B, and by tumor-specific cohorts for Part D, unless specified otherwise; a missing category will be included as applicable. Percentages will be calculated using the number of patients in the relevant population or subgroup as the denominator.

**Quantitative data:** (e.g., age, height, etc.) will be summarized by appropriate descriptive statistics (i.e. mean, standard deviation, median, minimum, and maximum) by study parts and by dose for Part A and Part C dose exploration, by age for Part A age expansion, by disease cohorts for Part B, and by tumor-specific cohorts for Part D, unless specified otherwise.

Note for age the derivation will be as follows:  $\text{round}(\text{date enrolled} - \text{birthdate} + 1) / 365.25$  to the nearest 0.1 decimal place.

Note for Pharmacokinetic reporting, age categorizations will be as follows: < 2 years, 2 to < 6, 6 to <12, and 12 to 18 years.

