#### Lab normal reference ranges

Local laboratory reference ranges will be collected throughout the study and will be provided by derived age at each visit using the age calculation algorithm provided in Appendix 5.14.

[figure not shown]

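### SAP Section 5.1.4 can assign the wrong age-specific laboratory range: a missing age is counted from zero at consent, and screening is aged by a different rule from later visits

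*SAP*

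**What the plan says.** SAP Section 5.1.4 works in two steps.

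- **Step 1, screening:** "Use the age that the site provided in raw data (Age in Days, Age in Months, Age in Years". Nothing is added to that age.
- **Step 1, other visits, age in years:** "Age at each visit is calculated as [Date of sample Collection(LBDT) - ICF date + Age in Years + 6 months".
- **Step 1, other visits, age in months:** "Age at each visit is calculated as [Date of sample Collection(LBDT) - ICF date + Age in Months + 15 days".
- **Step 1, other visits, age in days:** elapsed time since consent is added to the recorded days, with no further term.
- **Step 1, no age recorded:** "If age is missing in demo then age in each visit is calculated as [Date of sample Collection(LBDT) - ICF date".
- **Step 2:** this runs only where Step 1 mapped no range. It replaces the single age with a window. Its years branch begins: "If Age is provided in years, Age is [Date of sample Collection(LBDT) - ICF date + Age in Months - 6months". It has no branch for a missing age. Its worked example uses adjacent bands of 13-60 and 61-119.

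SAP Section 5.3 says the local reference ranges "will be provided by derived age at each visit using the age calculation algorithm". For demographic summaries, SAP Section 2.1 takes age from the enrolment date and the birth date (the sentence opening "Note for age the derivation will be as follows"), so birth date is already an analysis input.

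**The concern.** The derived age decides which lower and upper normal limits apply to a sample. Under SAP Sections 2.8.3 and 5.3 those limits set the low/normal/high class of tests without a CTCAE grade, any grade defined by a normal limit, and the liver criteria expressed as multiples of the ULN. These feed the shift tables from baseline to worst post-baseline value.

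The trial enrols from 1 month of age to adolescence, so time since consent cannot stand in for age in most of its children. Nothing in the output would show that it had been used: if the laboratory has an infant range, Step 1 maps it and Step 2 never runs. Separately, when a screening sample is the baseline, the two ends of a shift can be judged against different ranges although the child has hardly aged.

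Cohorts are small. In a cohort of 10, one child placed in the wrong class moves a reported rate by 1/10 = 10 percentage points.

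**Working it through.** **Inputs.** The rules are those of SAP Section 5.1.4. The month length is 30.4375 days (Section 2.1.1, Time unit). The example bands of 13-60 and 61-119 come from Step 2 and are read here as months. The SAP's own figures reproduce: 365.25/12 = 30.4375, and 14.3 months floors to 14.

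**1. Missing age.** Let A be true age at consent and t the time from consent to sample.

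- Assigned age = t. True age = A + t. Error = t - (A + t) = -A, whatever t is.
- A of 1 month, 2 years, 6 years and 12 years gives errors of -1, -24, -72 and -144 months.
- For A = 12 years and t = 365 days: assigned 365/30.4375 = 12.0 months; true 144 + 12.0 = 156.0 months.

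Time runs from consent here, not from first dose, because that is how the rule is written.

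**2. Screening against later visits, age in years.** Assume the site records completed years, which the SAP does not state. True age at consent is then 12Y + f months, where Y is the recorded age and f is uniform between 0 and 12. Take screening as being at consent.

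- Screening: assigned 12Y, error -f. Mean -6 months, range -12 to 0, mean absolute error 6.
- Later: assigned 12Y + 6 + t, true 12Y + f + t, error 6 - f. Mean 0, range -6 to +6, mean absolute error 3.
- Between screening and the next visit, assigned age rises by elapsed time plus 6 months. For ages in months the extra step is 15/30.4375 = 0.49 months. For ages in days it is zero.

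Applied to the example bands:

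- **Recorded 5 years:** 5 x 12 = 60 at screening, in band 13-60. At 28 days after consent, 60 + 6 + 28/30.4375 = 66.9, in band 61-119. True completed months reach 61 when f is 1 or more. The screening band is therefore wrong for 11/12 = 92% of such children and the later band for 1/12 = 8% (ignoring elapsed time).
- **Recorded 4 years:** 48, then 54 plus elapsed time. At these early visits both ages are in band 13-60, and no child is misplaced.
- **Recorded 10 years:** 120, then 126 or more. Both are above 119, and the SAP shows no band edge there, so no change of range can be demonstrated.

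**3. Step 2, years branch.** For a recorded 5 years:

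- Converted to months first: 60 - 6 = 54 to 60 + 6 = 66, plus elapsed time.
- With 5 entered as months, as the text permits: 5 - 6 = -1 to 5 + 6 = 11, plus elapsed time.

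The two steps also imply different recording conventions. Adding half a unit in Step 1 fits ages recorded as completed units; the symmetric window in Step 2 fits ages rounded to the nearest unit.

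**The case against.** The strongest reply is that little may change in practice.

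- **The missing-age group may be empty.** Enrolment is by age and Section 2.1 uses birth date, so a child without an age should be exceptional. This stands as a limit on frequency. It does not defend the rule, which gives a wrong age for any child it touches.
- **The 6 months are a sensible midpoint.** If sites record completed years, this is right: the addition removes a mean bias of 6 months. A reader might infer that adding 6 months is the error. The fault is leaving it out at screening.
- **Baseline need not be the screening sample.** Section 2.1.1 takes the last assessment on or before the start of treatment. A later pre-dose sample would follow the same rule as follow-up, so the mismatch arises only where a screening sample is the baseline.
- **The Step 2 wording is a slip with an obvious meaning.** Probably so, and it matters only where Step 1 mapped nothing. It should still be corrected, because a program is written from this text.
- **Much of the safety analysis is untouched.** This stands. Change from baseline (Section 2.1.1) uses no normal range, nor do the liver criteria expressed only as multiples of baseline (Section 2.8.3). DLTs are investigator-assessed events judged against protocol criteria (Section 2.8.1). All analyses are descriptive.

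**Conclusion.** The rules in Section 5.1.4 are wrong or inconsistent as written and can assign the wrong laboratory range. The missing-age rule is the clearest fault: its error equals the child's whole age at consent, up to many years, and no later step catches it. The screening rule differs from the later-visit rule by 6 months for ages in years and 15 days for ages in months. The years branch of Step 2 names the wrong unit.

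A reader might infer that reference ranges and laboratory grades will be wrong across the trial. The SAP does not support that. A class or grade changes only if three things hold together: it depends on the LLN or ULN, the age error crosses a band edge in that laboratory's ranges, and the value lies between the two alternative limits (or their stated multiples). The local bands are not in the SAP and the number of children without a recorded age is not given, so the number of affected results cannot be estimated. The 92% and 8% figures rest on completed years, ages spread evenly within the year and the SAP's example bands. They describe children recorded at a band edge, not the whole trial.

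**What to change.** Amend Section 5.1.4 as follows.

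1. Derive age at each sample as sample date minus birth date, at all visits including screening.
2. Where only a recorded age is available, apply the same midpoint rule at screening and at later visits. On the completed-years assumption this moves the mean screening error from -6 to 0 months (range from -12 to 0, to -6 to +6) and removes the 6-month step.
3. Where age is missing, leave the range unmapped and raise a query. Delete the rule that uses time since consent.
4. In the years branch of Step 2, replace age in months with age in years converted to months, -/+ 6 months. State whether recorded ages are completed or rounded, so that Step 1 and Step 2 follow one convention.

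The cost is a few lines of SAP text and a simpler derivation program, with the range mapping rerun. No new data are needed where birth date is held. If no child lacks an age, deleting the missing-age rule changes no result.
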